## **7.2 PHARMACODYNAMIC ASSESSMENTS**

Temperature readings will be performed at least 4 times daily through the end of treatment (morning, mid-day, late afternoon, and evening; approximately every 4 hours during waking hours). Temperature will be measured orally and recorded in a patient diary (and given to the site coordinator for entry in the eCRF).

A rapid point of care (POC) test for DENV NS1 antigen and a DENV serotype test will be performed at screening. Viral load will be assessed by measuring plasma viremia by viral titre and with a serotype-specific, real-time reverse transcription PCR assay at screening and on Days 1-8, Day 14, and Day 28. DENV NS1 will be measured by ELISA at screening and on Days 1-8, Day 14, and Day 28. See [Section 3.1.4](#) for a description of the timing for collection of these samples.

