### **8.3.4 Pharmacodynamic Exploratory Analyses**

- Change in DENV viral load (as measured by viral titre) from baseline
- Area under the log10-transformed viral load curve (AUC) from first dose to the end of treatment (Day 5-6) and to study end (Day 28) (as measured by DENV RNA and viral titre)

- Time to viral load (as measured by DENV RNA and viral titre) or NS1 clearance, defined as time to first of 2 consecutive undetectable viral load or NS1, will be described using Kaplan-Meier methods. The median time to viral clearance and the estimated proportions of patients with viral clearance will be summarized by treatment group. Patients who do not receive a record a negative test result by RT-PCR/viral titre or NS1 antigen assay by the last observation timepoint will be treated as censored at the final scheduled evaluation time point.
- Change of DENV viral load (as measured by DENV RNA and viral titre) from baseline, viral load AUC, time to viral load or NS1 clearance by DENV serotype
- Treatment-emergent amino acid substitutions in DENV NS5 gene
- 
- Methods for analysis of time to resolution or duration of fever will be presented in the SAP
- Exploratory biomarkers may include plasma concentrations of cytokines (for example, TNF- $\alpha$ , IFN- $\gamma$ , IL-2, IL-4, IL-5, IL-6, IL-10, IL-12, IL-13, IL-1 $\beta$ , IP-10 and MCP-1)
- Exploratory analyses may be performed to evaluate exposure-response relationship. The relationship between the exposure of AT-752 (and its metabolites) and DENV viral load may be explored using graphical displays

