#### **4.1. Sample Size**

The sample size for this study is up to 60 subjects and each cohort will include 20 subjects, allocated 3:1 (AT-752:placebo). In Low et al (Low 2014), the observed standard deviations (SD) for VLR, defined as mean change from baseline viral load on days 2,3, and 4, ranged from 0.75 (N=26) to 1.07 (N=24). Taking into account that the VLR endpoint in the study was based on an average of 3 measurements and assuming that there is some correlation between measurements on days 2 through

4, we consider power to detect a true effect at a single time point using a one-sided 0.10 level test (unadjusted for multiple comparisons) with N=15 per arm for SD in a range from 1 to 1.75:

True standard deviation	Effect (log 10 copies/ml) with 80% power (N=15 vs. 15)	Effect (log 10 copies/ml) with 80% power (N=15 vs. 5)
1	0.8	1.1
1.25	1	1.4
1.5	1.2	1.7
1.75	1.4	2.0

Based on the above table, there is 80% power to detect a true treatment effect (versus placebo) on change-from-baseline viral load of 1 log10 at a time point if the true SD is 1.25 for comparison of groups with N=15 each. The analogous power to detect a 1 log10 effect for a within cohort comparison is 59%. Furthermore, if true SD is in the range from 1 to 1.75, the probability that the observed effect would be 0.5 log10 or larger is low (in range from 0.09 to 0.22) if there is no treatment effect, i.e., an observed effect of 0.5 or larger might be considered suggestive of a signal. Interpretation of results will consider the totality of the data.

In the event there is at least one subject who withdraws without post-baseline virology data, with the exception of those who withdraw for safety or tolerability, enrollment may remain open or extended at each dose level/cohort to enroll additional randomization block(s) of 4 patients (3:1) to increase the likelihood that at least 15 active and 5 placebo subjects with evaluable virology data are included in each cohort. Any additional patients will be randomized through the same centralized randomization process. All statistical analysis will be based on actual enrolled subjects.

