### 10. Missing data handling

In general, observed data will be used in statistical analysis without imputation, unless missing data will jeopardize the integrity of the study or pose a problem in the validity of the analysis. A data-as-observed (DAO) approach will be used to evaluate the primary endpoint. Uncertain viral load measurements that are below the lower limit of quantification (LLOQ) will be set to  $0.5 \times \text{LLOQ}$  in the viral load summaries and indicated as BLQ in the listings. If subjects withdraw early, the outcome measure up to point of study withdrawal will be used.

Impact of missing data will be assessed, and ad-hoc sensitivity analysis will be performed when deemed appropriate. No imputation is planned for the primary efficacy analysis, as the study allows replacement when a subject withdraws without any post-baseline virology data and a mixed model will be used. If at a particular time point, the amount of missing data in the AT-752 arm is greater than 10% due to dropout, the impact will be assessed. In this case, an ad-hoc sensitivity analysis using multiple imputations will be performed using the Markov chain Monte Carlo (MCMC) method to impute non-monotone missing data, and a copy reference (i.e. placebo) approach to impute monotonic missing data in the AT-752 arm.

For safety data, missing and partial dates will be programmatically handled according to the following standards: if the day of the month is missing for any date used in a calculation, the 1st of

the month will be used to replace the missing date unless the calculation results in a negative time duration (e.g., date of resolution cannot be prior to date of onset; if replacing resolution date with the 1st of the month results in a negative duration, the resolution date will be set to the onset date). In this case, the date resulting in 0 time duration will be used. These standards are also used if both month and day are missing (Jan 1 unless negative time duration, durations will be reset to 1 day).

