Intermediate missing log 10-transformed viral loads (between baseline and the last day) will be linearly interpolated using the last and next available viral loads for AUC calculation for both AUCD5 and AUCD28. Subjects with intermediate missing values will be included in AUC analysis.

Time to viral load (as measured by DENV RNA and viral titre) or NS1 clearance, defined as time to first of 2 consecutive results of undetectable viral load or NS1, will be described using Kaplan-Meier methods. The median time to viral clearance and the estimated proportions of patients with viral clearance will be summarized by treatment group. Patients who do not receive a record of a negative test result by RT-PCR/viral titre or NS1 antigen assay by the last observation timepoint will be treated as censored at the final scheduled evaluation time point.

Subgroup analysis by DENV serotype will be carried out for the following endpoints: change of DENV viral load (as measured by DENV RNA and viral titre) from baseline, viral load AUC, time to viral load or NS1 clearance. Descriptive statistics (N, mean, standard deviation, median, minimum and maximum, and 95% CI) will be presented by treatment group.

Number and percentage of subjects with treatment-emergent amino acid substitutions in DENV NS5 gene will be compared between the treatment groups (chi-squared test).

Duration of fever is the sum of fever episode durations where fever episode duration is defined as the time from first fever measurement (either at baseline or following a period without fever) to the next measurement without fever. If the last episode has not resolved, duration for that episode will be

censored at the time of the last temperature measurement. Treatments will be compared by log-rank test.

Exploratory biomarkers may include plasma concentrations of cytokines (for example, TNF- $\alpha$ , IFN- $\gamma$ , IL-2, IL-4, IL-5, IL-6, IL-10, IL-12, IL-13, IL-1 $\beta$ , IP-10 and MCP-1). Data will be presented in descriptive statistics by treatment.

Exploratory analyses may be performed to evaluate exposure-response relationship. The relationship between the exposure of AT-752 (AT-281 and its metabolites AT-551, AT-229, and AT-273) and DENV viral load may be explored using graphical displays. Scatter plots of drug exposure versus change in DENC viral load will be provided.

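### The censoring date for time to clearance names no day, most naturally means Day 28 even for patients who left earlier, and leaves a single unconfirmed negative without a rule

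*SAP*

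**What the plan says.** SAP Section 12 describes time to clearance of DENV RNA, viral titre and NS1 by Kaplan-Meier, reporting the median and the proportion cleared by treatment group. The event time is "defined as time to first of 2 consecutive results of undetectable viral load or NS1". The censoring sentence begins "Patients who do not receive a record of a negative test result" and ends "by the last observation timepoint will be treated as censored at the final scheduled evaluation time point". Protocol Section 8.3.4 has the same rule: such patients "will be treated as censored at the final scheduled evaluation time point".

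Neither sentence names a day. Protocol Section 7.2 gives the sampling plan: "DENV NS1 will be measured by ELISA at screening and on Days 1-8, Day 14, and Day 28". Viral load follows the same days. In the schedule of events (Protocol Table 3-1), the last column serves both Day 28 and early termination, and it limits viral load and NS1 to the Day 28 visit.

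Three other rules bear on early leavers:

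- **Fever, SAP Section 12.** An unresolved last fever episode is "censored at the time of the last temperature measurement".
- **Missing data, SAP Section 10.** "If subjects withdraw early, the outcome measure up to point of study withdrawal will be used".
- **Replacement, SAP Section 4.1.** Extra enrolment is possible "In the event there is at least one subject who withdraws without post-baseline virology data", with safety and tolerability withdrawals excepted.

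**The concern.** Censoring should end a patient's time at risk when observation ends. If the sentence means Day 28 for everyone, a patient last sampled on Day 5 and still positive counts as observed and uncleared for another 23 days. Each later risk set is then too large by one, and the estimated clearance curve is pulled down in whichever arm loses such patients.

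The second difficulty needs neither dropout nor the Day 28 reading. The event requires two consecutive undetectable results, while the censoring rule is triggered only by having no negative result. A patient who completes the study, is positive on Day 14 and is first negative on Day 28 has no event and is not covered by the censoring sentence. The same applies to a leaver whose last sample is the first negative, and to isolated negatives that are never consecutive. The programmer would have to supply a rule. SAP Section 4 defers analysis until the data are unblinded, so that choice could be made with treatment known.

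At stake are the exploratory clearance summaries for three assays.

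**Working it through.** The documents give no figure for time to clearance, no dropout rate and no clearance times, so there is no plan figure to reproduce. The planned arm size is 15 (15 active per cohort, and 15 placebo pooled over three cohorts). Everything else below is assumed for illustration.

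**1. Which day.** The sentence uses two terms, one for the last observation and one for the last scheduled evaluation. Set against each other, the second points to the end of the schedule, which is Day 28.

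**2. Does another rule repair it?** Replacement is triggered only by patients with no post-baseline virology, so a leaver with some data stays in the analysis. Protocol Section 4.3.2 asks for end-of-study assessments where possible, but Table 3-1 requires no virology sample at early termination.

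**3. Direction and bound.** Kaplan-Meier gives S(t) = product over event days of (1 − d/n), with d events among n at risk. Moving a leaver's censoring date to Day 28 leaves every d unchanged and makes some n larger, so the proportion cleared, 1 − S(t), cannot rise. With c patients cleared by time t and no other censoring, the Day 28 reading gives c/15. Last-sample censoring gives at most (c + k)/15 for k uncleared leavers. The loss therefore lies between 0 and k/15: at most 6.7, 13.3 and 20.0 points for k = 1, 2, 3.

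**4. Illustration A.** Assumed clearance days without dropout: 4, 5, 5, 6, 6, 6, 6, 7, 7, 7, 8, 8, 8, 14, 14. The patients clearing on {7}, {6, 7} or {6, 7, 8} become uncleared leavers last sampled on Day 5. S at Day 8 with last-sample censoring:

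- k = 1: (14/15)(12/14)(7/11)(5/7)(2/5) = 0.1455
- k = 2: (14/15)(12/14)(7/10)(5/7)(2/5) = 0.1600
- k = 3: (14/15)(12/14)(6/9)(4/6)(2/4) = 0.1778

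| k | Cleared by Day 8, last-sample | Cleared by Day 8, Day 28 reading | Loss (points) |
|---|---|---|---|
| 1 | 85.5% | 12/15 = 80.0% | 5.5 |
| 2 | 84.0% | 11/15 = 73.3% | 10.7 |
| 3 | 82.2% | 10/15 = 66.7% | 15.6 |

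The median is Day 7 under both rules.

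**5. Dependence on the last sample day (Illustration A, k = 1).** The Day 28 reading gives 80.0% at Day 8 in every column.

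| Last sample day | 5 | 6 | 7 | 8 | 14 |
|---|---|---|---|---|---|
| Loss at Day 8 (points) | 5.5 | 4.8 | 4.0 | 0 | 0 |
| Final loss, all others clear by Day 14 | 6.7 | 6.7 | 6.7 | 6.7 | 0 |
| Final loss, the two Day 14 patients stay uncleared to Day 28 | 5.5 | 4.8 | 4.0 | 0 | 0 |

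On nominal days the latest possible event is Day 14, confirmed on Day 28. Only leavers last sampled on Day 8 or earlier can therefore change the estimate.

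**6. Illustration B.** A different assumed arm (4, 5, 5, 6, 6, 6, 7, 7, 7, 8, 8, 8, 14, 14, 14), with leavers last sampled on Day 3. For k = 2 the patients assumed to clear on Days 6 and 7 leave, and 10 of the remaining 13 clear by Day 8. Last-sample censoring gives 10/13 = 76.9%, and the Day 28 reading gives 10/15 = 66.7%. By Day 7, 7 have cleared: 7/13 = 53.8% against 7/15 = 46.7%. The median therefore moves from Day 7 to Day 8. Whether the median shifts depends on the clearance times.

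**7. Single negative.** The event condition is two consecutive undetectable results, and the censoring condition is no negative result. These do not cover all patients: anyone with at least one negative but no consecutive pair meets neither condition.

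**The case against.** The sentence can be read as addressing only patients followed to the end without a negative, for whom Day 28 is the ordinary censoring date. Early leavers would then fall under SAP Section 10. This reading is possible, and it is why the point is about an unnamed date. It does not settle the matter, because SAP Section 10 says which data are used and gives no censoring date, and Kaplan-Meier needs one.

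A reader might infer that the plan contradicts itself over fever, or that SAP Section 10 already requires last-sample censoring. The documents support neither. The fever rule governs another endpoint, and both rules can be carried out as written, so the mismatch is an inconsistent convention. SAP Section 10 is compatible with last-sample censoring but does not prescribe it, so the Day 28 reading only sits uneasily beside it.

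It is also fair to say that the negative-result wording may be shorthand for the two-result event, and that a patient without an event must be censored somewhere. That stands, but the date is still missing.

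Last, the cases may be few. Protocol Section 4.3.2 encourages patients who stop treatment to stay on schedule, and with no uncleared leavers the two rules agree.

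**Conclusion.** The point holds as a drafting gap of low severity with two parts: the censoring date is unnamed and most naturally Day 28, and a single unconfirmed negative has no stated censoring time.

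Relative to last-sample censoring, the Day 28 reading loses between 0 and k/15 of the proportion cleared and may delay the median. The bound needs only the arm size. The specific percentages rest on invented clearance and dropout patterns and are not predictions.

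A reader might infer that the plan is biased against the drug, or that the efficacy conclusion is at risk. The documents do not support that. The primary mixed model on DENV RNA does not use this rule, no between-arm test of clearance is planned, and SAP Section 4 treats all intervals and p-values as descriptive. Nor is the lower figure necessarily the wrong one: calling it a downward bias assumes that leaving is unrelated to clearance. If leavers clear more slowly, last-sample censoring overstates clearance and the Day 28 version is the cautious one.

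**What to change.** In SAP Section 12, replace the censoring sentence with:

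*Patients without two consecutive undetectable results are censored at the date of their last available assessment of that assay.*

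Apply it separately to RNA, titre and NS1. Tying censoring to the absence of two consecutive undetectable results is deliberate: it matches the event definition and covers the single unconfirmed negative. The rule also follows the same convention as the fever rule.

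SAP Section 14 now states that nothing departs from the protocol. Record the change there, and align Protocol Section 8.3.4 at the next amendment. The Day 28 version can be kept as a sensitivity summary, because last-sample censoring assumes that leaving is unrelated to clearance.

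The cost is one sentence, one entry in SAP Section 14 and a later protocol edit. No new data are needed. The wording should be settled before unblinding.

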### **3.1.4 Timing of Samples for PK, Viral Load, and NS1**

The timing of samples for PK analyses, viral load determination, and NS1 levels are outlined below for TID and for BID dosing. As shown in the tables below, the timing will vary depending on the time of day that the patient received Dose 1 of study medication and how many doses of study medication they received on Day 1.

10. Timing of sample collections for patients who begin TID dosing at different times on Day 1 and thus receive either 3 doses, 2 doses, or 1 dose of study medication on Day 1, are provided in [Table 3-2](#), [Table 3-3](#), and [Table 3-4](#), respectively. In these tables, Day 1 is the day of dosing. Some of the PK sample times are fixed (pre-dose on Day 1, 24 hours after Dose 1), and some are flexible (serial PK samples for TID dosing may be obtained at either dose 7, 8, or 9). Some of the virology sample times are fixed (pre-dose on Day 1, 24 hours after Dose 1, 48 hours after Dose 1, and 8-24 hours after Dose 15). Other virology sample times are flexible, with samples collected anytime on each of 6 days (Days 4, 5, 7, 8, 14, and 28).
11. Timing of sample collections for patients who begin BID dosing at different times on Day 1 and thus receive either 2 doses or 1 dose of study medication on Day 1, are provided in [Table 3-5](#) and [Table 3-6](#), respectively. In these tables, Day 1 is the day of dosing. Some of the PK sample times are fixed (pre-dose on Day 1, 24 hours after Dose 1), and some are flexible (serial PK samples for BID dosing may be obtained at either dose 5, 6, or 7). Some of the virology sample times are fixed (pre-dose on Day 1, 24 hours after Dose 1, 48 hours after Dose 1, and 8-24 hours after Dose 10). Other virology sample times are flexible, with samples collected anytime on each of 6 days (Days 4, 5, 7, 8, 14, and 28).

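### SAP 12 prescribes ordinary descriptive statistics for time to clearance by serotype, a right-censored endpoint, and does not say how censored subjects enter the summary

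*SAP*

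**What the plan says.** SAP section 12 (Pharmacodynamics) covers time to clearance twice, in consecutive paragraphs.

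- **Overall analysis.** The endpoint is "defined as time to first of 2 consecutive results of undetectable viral load or NS1" and "will be described using Kaplan-Meier methods". The outputs are the median and the estimated proportion cleared, by treatment group. Subjects with no negative result "will be treated as censored at the final scheduled evaluation time point".
- **Serotype subgroups.** "Subgroup analysis by DENV serotype will be carried out for the following endpoints": change in viral load, then "viral load AUC, time to viral load or NS1 clearance". The next sentence gives the only method: "Descriptive statistics (N, mean, standard deviation, median, minimum and maximum, and 95% CI) will be presented by treatment group". It has no exception for the clearance endpoints and does not mention Kaplan-Meier or censoring.

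The protocol supplies no alternative. Its section 8.3.4 lists "time to viral load or NS1 clearance by DENV serotype" without a method, as do the synopsis and section 6.4. SAP section 4 makes the same kind of list the default for continuous data unless otherwise specified, and describes the study's analyses as descriptive.

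**The concern.** Mean, SD, maximum and an ordinary CI assume that every time in the list was observed. Time to clearance need not meet that condition here:

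- Clearance needs two consecutive undetectable results, so a first undetectable result on Day 28 cannot be confirmed.
- Subjects may withdraw. The schedule of events marks viral load and NS1 at the final visit for Day 28 only, so an early-termination visit adds no virology sample.

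The subgroup sentence is the only instruction for these tables. A programmer must choose between entering censored subjects at some time, leaving them out, and carrying Kaplan-Meier over from the paragraph above.

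The protocol's rationale is a therapy active against all serotypes, and these are the only planned serotype-specific clearance summaries. Each active arm has 15 subjects and pooled placebo has 15. Split evenly over four serotypes (an assumption, since no serotype mix is given), that is 15/4 = 3.75 subjects per cell. In cells that small, one censored subject can move a mean by days.

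**Working it through.** The documents give no clearance rate, censoring rate or serotype mix, so there is no planned figure to reproduce. The two checks below are illustrations.

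**1. A five-patient cell (constructed).** Times are study days. Three subjects clear on Days 4, 5 and 6; one leaves at Day 3 still positive; one is still positive at Day 28.

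Ordinary summaries, with CI = mean ± t × SD/√n:

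| Handling of censored subjects | Mean | SD | 95% CI | Median |
|---|---|---|---|---|
| Omitted | (4+5+6)/3 = 5.0 | 1.0 | 5.0 ± 4.303×1.0/√3 = 2.5 to 7.5 | 5 |
| Leaver at Day 3 | (3+4+5+6+28)/5 = 9.2 | 10.6 | 9.2 ± 2.776×10.57/√5 = −3.9 to 22.3 | 5 |
| Leaver at Day 28 | (4+5+6+28+28)/5 = 14.2 | 12.6 | 14.2 ± 2.776×12.62/√5 = −1.5 to 29.9 | 6 |

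Kaplan-Meier on the same subjects, with the median taken as the first time survival is 0.5 or less:

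- Leaver censored at Day 3: S(4) = 3/4 = 0.75; S(5) = 0.75×2/3 = 0.50; S(6) = 0.50×1/2 = 0.25. The median is Day 5. Restricted mean to Day 28 = 4 + 0.75 + 0.50 + 0.25×22 = 10.75.
- Leaver censored at Day 28: S(4) = 0.8; S(5) = 0.6; S(6) = 0.4. The median is Day 6. Restricted mean = 4 + 0.8 + 0.6 + 0.4×22 = 14.2.

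Compared like with like, the mean is 9.2 against 10.75 with the leaver at Day 3, and 14.2 against 14.2 with the leaver at Day 28. The medians agree in both cases (5 and 5; 6 and 6). Omitting censored subjects gives a mean of 5.0, well below either restricted mean. Two of the three ordinary intervals include negative times, and one runs past Day 28.

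**2. Large-sample behaviour (simulated).** The inputs from the documents are virology on Days 2 to 8, 14 and 28 and the two-consecutive rule. The assumptions are exponential clearance with the true medians shown, and dropout of 0 or 20%. Each scenario has 200,000 subjects, and times are days since first dose, so Day 28 is 27.

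| True median | Dropout | Handling | Censored | Ordinary mean | Restricted mean | Ordinary median | Kaplan-Meier median |
|---|---|---|---|---|---|---|---|
| 5 | 0 | All at Day 28 | 17% | 9.43 | 9.43 | 6 | 6 |
| 5 | 0 | Omitted | 17% | 5.92 | 9.43 | 4 | 6 |
| 5 | 20% | Own last visit | 26% | 8.26 | 9.68 | 5 | 6 |
| 8 | 0 | All at Day 28 | 32% | 13.30 | 13.30 | 13 | 13 |
| 8 | 0 | Omitted | 32% | 6.72 | 13.30 | 5 | 13 |
| 8 | 20% | Own last visit | 41% | 11.43 | 13.54 | 7 | 13 |
| 20 | 0 | All at Day 28 | 64% | 19.95 | 19.95 | 27 | Not reached |

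The medians move on the visit grid. The step from 7 to 13 reflects the gap between Day 8 and Day 14. A true median of 5 falls on a visit, so a one-day difference there carries little weight.

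**The case against.** The strongest reply is that the subgroup sentence is one general line covering several endpoints, and that it suits change from baseline and AUC. It does not revoke the definition and censoring rule given just above it, so a sensible programmer could carry Kaplan-Meier over. On the plain reading of that rule, non-clearers sit at Day 28. The ordinary median then equals the Kaplan-Meier median while fewer than half are censored, and the ordinary mean equals the restricted mean. With no censoring in a cell, there is no censoring bias. Subject-level data are listed and individual viremia profiles are planned, so a reader could recover much of the detail. The analysis is an exploratory subgroup with no test specified.

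Most of this stands, and it limits the size of the point. It does not remove it. The sentence names a method for the clearance endpoints, and that method is not Kaplan-Meier. Even with every non-clearer at Day 28, the mean is a restricted mean that the table would not label as such, the maximum is the cut-off, and the SD is driven by it. The listings and profiles carry no stated censoring flag for clearance.

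**Conclusion.** The point holds as an unsuitable summary combined with an unstated rule. If any subject in a serotype-by-treatment cell is censored, the mean, SD, maximum and CI do not describe clearance time. In the five-patient example the mean ranges from 5.0 to 14.2 according to the handling chosen. The ordinary median is wrong when censored subjects are omitted, can be too early when leavers are placed at their last visit, and misleads when half or more are censored.

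Three stronger readings are tempting, and the documents do not support them:

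- **That the SAP counts censored times as observed clearances, and so gives wrong results.** It never says so. Omission and Kaplan-Meier are equally open, and any bias requires censoring within the cell.
- **That the error is the gap between a mean of 9.2 or 14.2 and a Kaplan-Meier median of 5 or 6.** That compares a mean with a median in skewed data. Like for like, the medians agree and the means differ only in the early-leaver coding, by 10.75 − 9.2 = 1.55 days.
- **That serotype differences would reflect follow-up instead of clearance.** No censoring rate or serotype mix is given, all arms share the same virology days, and subjects who stop treatment are encouraged to stay on schedule.

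The analysis is exploratory and descriptive. The primary endpoint, safety, PK and the overall clearance analysis are unaffected. The sizes above rest on a constructed example and assumed clearance and dropout rates.

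**What to change.** In SAP section 12, confine the mean, SD, median, minimum, maximum and 95% CI to change from baseline and AUC by serotype. Add one sentence saying that time to viral load and NS1 clearance by serotype uses the Kaplan-Meier method and censoring rule of the overall analysis. It should report the median, the estimated proportion cleared, and the numbers cleared and censored. Where cells are very small, show individual times with a censoring flag; the team can set the cell-size threshold and any landmark days.

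The cost is a one- or two-sentence edit before unblinding. The Kaplan-Meier method is already specified for the overall analysis, and no new data are needed.
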